8.4.4 Pharmacokinetic Analyses

The nivolumab, ipilimumab, BMS-986016, and daratumumab concentration data obtained in this study may be combined with data from other studies in the clinical development programs to develop or refine a population PK model. These models may be used to evaluate the effects of intrinsic and extrinsic covariates on the PK of nivolumab or other compounds and to determine measures of individual exposure. In addition, model determined exposures may be used for exposure-response analyses. If performed, results of population PK and exposure response-analyses will be reported separately.

8.4.5 Biomarker Analyses

Methodology for exploratory biomarker analyses, including characterization of discordant rates for MSI testing, is described in the statistical analysis plan.

8.4.6 Outcomes Research Analyses

EO 5D

Subject's overall health state on a visual analog scale (EQ-VAS) at each assessment time point will be summarized using descriptive statistics, for each cohort assessed, by treatment (monotherapy and combination therapy, if applicable). The proportion of subjects reporting problems for the 5 EQ-5D dimensions at each assessment time point will be summarized by level of problem each cohort by treatment (monotherapy and combination therapy, if applicable). Percentages will be based on number subjects assessed at assessment time point.

A by-subject listing of EQ-5D with the problem levels for each of the 5 dimensions (mobility, self-care, usual activities, pain/discomfort and anxiety/depression), health state (5 dimensions digits combined in a 5-digit number), and EQ-VAS will be provided.

EORTC QLQ C-30

The analysis of EORTC QLQ C-30 will be performed in all treated subjects in each cohort who have an assessment at baseline and at least one follow-up assessment.

All scales and single items are scored on a categorical scale and linearly transformed to 0-to-100 scales with higher scores for a functional scale representing higher levels of functioning, higher scores for the global health status/quality of life representing higher levels of global health status/quality of life, and higher scores for a symptom scale representing higher level of symptoms. EORTC QLQ C-30 global health status/QoL composite scale data and the remaining EORTC QLQ C-30 scale data will be summarized by time point using descriptive statistics for each cohort assessed.

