- To evaluate health-related quality of life using a validated instrument in the European Organisation for Research and Treatment of Care General Cancer Module (QLQ-C30).
- To evaluate patient reported general health status as assessed by the five item EQ-5D.
- To evaluate clinical activity and safety of nivolumab monotherapy or combination treatment after re-initiation.

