Targeted Physical Examination	X	Targeted examination must include at a minimum the following body systems: Cardiovascular Gastrointestinal Pulmonary Neurological exam for subjects with brain metastases	
Vital Signs	X	Including BP, HR, and temperature. Obtain vital signs within 72 hours prior to first dose.	
Physical Measurements (including performance status)	X	Weight and ECOG performance status. See Appendix 2 for ECOG Performance Status scale.	
Review of Concomitant Medication	X		
Adverse Events Assessment	X		
Laboratory Tests	X	On-study local CBC, chemistry, and thyroid laboratory assessments (after first dose) should be done within 72 hours prior to each dose and include: CBC w/differential and platelet count, LFTs (ALT, AST, total bilirubin, alkaline phosphatase), BUN or serum urea level, creatinine, Ca, Mg, Na, K, Cl, LDH, glucose, amylase, lipase, TSH with reflexive Free T4, Free T3.	
Pregnancy Test (WOCBP only)	X	Serum or urine pregnancy test to be done within 24 hours prior to first dose, and then every 4 weeks (± 1 week) regardless of dosing schedule	

Table 5.1-2: Short-Term Procedural Outline (Nivolumab Monotherapy, CA209142): MSI-H (Arm N, mStage 1/2)			
Procedure	During Treatment Day 1 every 4 weeks See Section 3.1.4.1 for treatment duration	Notes Visit Window : ± 2 Days	
Efficacy Assessments			
Tumor Imaging Assessment		See separate Table 5.1-14	
Outcomes Research Assessment			
EORTC QLQ-C30 & EQ-5D Questionnaires	Assessed following drug vial assignment but before first dose and every 6 weeks when coinciding with clinic visits. Assessed at follow-up visit 1 & 2. Assessments should be completed at the start of the study visit prior to any study-related procedures or speaking with the physician.		
Pharmacokinetic Assessments	For all subjects, except for those enrolled in the non-MSI-H Safety Cohort		
Nivolumab PK blood sample	See separate Table 5.5.1-2		
Immunogenicity Assessments			
Nivolumab Immunogenicity blood sample collection	See separate Table 5.5.1-2		
Exploratory Biomarker Testing			
Soluble Biomarkers (Serum)	See separate Table 5.6.8-1		
Peripheral Blood Mononuclear Cells (PBMCs) Immuno-phenotyping	See separate Table 5.6.8-1		
Ex vivo Functional assay (PBMCs)	See separate Table 5.6.8-1		
Tumor tissue sample (biopsy)	See separate Table 5.6.8-1		
Whole blood gene expression	See separate Table 5.6.8-1		
Stool sample	See separate Table 5.6.8-1		
Plasma Sample	See separate Table 5.6.8-1		
SNP (whole blood)	See separate Table 5.6.8-1		

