Table 5.1-6: Short-term Procedural Outline for C6 Cohort [Nivolumab + Daratumumab] non-MSI-H

Procedure	To Be Performed at Each Dosing Visit, Unless Otherwise Specified in Notes or Separate Table	Notes Visit Window : ± 2 Days
		The dosing calculations should be based on the body weight. All doses should be rounded to the nearest milligram.

Procedure	Follow Up, Visits 1 and 2 ^a	Survival Follow-Up Visits ^b	Notes
Safety Assessments			
Targeted Physical Examination	X		To assess for potential late emergent study drug related issues
			Targeted examination must include at a minimum the following body systems:
			Cardiovascular
			Gastrointestinal
			Pulmonary
			Neurological exam for subjects with brain metastases
Adverse Events Assessment	X		In Survival Follow-Up period only to include toxicities from study therapy
ECG	X		Only at FU1
Review of Concomitant Medication	X	X	Subsequent Cancer Therapy
Laboratory Tests	Х		CBC w/ differential and platelet count, LFTs, BUN or serum urea level, creatinine, Ca, Mg, Na, K, Cl, LDH, Glucose, amylase, lipase, TSH (+ reflex Free T4 and Free T3)
			To be done at FU1. To be repeated at FU2 if study related toxicity persists.
Troponin	X	X*	Performed for the C5 Cohort Only. All results should be checked as soon as possible.
			*Troponin testing as clinically indicated, at the discretion of the treating physician during survival follow-up.
Pregnancy Test (WOCBP only)	X		Serum or urine
Efficacy Assessments			
Tumor Imaging Assessment	See note	See note	Refer to Figure 3.1.4.8-1.
rumor imaging Assessment	See note	See note	See separate Table 5.1-14

Table 5.1-7: Follow-Up Period (All treatment groups, CA209142)			
Procedure	Follow Up, Visits 1 and 2 ^a	Survival Follow-Up Visits ^b	Notes
Outcomes Research Assessment			
EORTC QLQ-C30 & EQ-5D Questionnaires	X	X*	For all subjects except subjects in independent non-MSI safety cohort. *Only EQ-5D Questionnaire is required at Survival Follow-Up Visits
Herpes Zoster Virus Antiviral Prophylaxis	X		See Section 3.4.2.3 Initiate antiviral prophylaxis within 1 week after starting daratumumab. Continue antiviral prophylaxis during the Treatment Phase as per institutional guidelines, and for 3 months following treatment discontinuation.
Subject Status			

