8.2 Populations for Analyses

- The following definitions will apply to all cohorts except where otherwise specified:
- The MSI-H cohort will include subjects who are defined as MSI-H based on standard diagnostic testing documented in the subject's medical history (MSI-H per local testing) including those prospectively confirmed in the current study by repeat testing using a PCR test. Subjects in this cohort will be referred to as 'confirmed MSI-H subjects.' Similarly, the non-MSI-H cohort will include all subjects testing non-MSI-H by the repeat PCR test or standard diagnostic testing documented in the subject's medical history.
- All Treated Subjects: All subjects who received at least one dose of study medication within a cohort. This is the primary population for safety and efficacy analysis in any cohort.
- All response evaluable subjects: All treated subjects within a given cohort who have baseline and at least one on-study evaluable tumor measurement.
- PK subjects: All subjects with available serum time-concentration data from subjects dosed with study drug.
- Immunogenicity subjects: all treated subjects with available immunogenicity data.

• PD-L1 measurable subjects: all treated subjects with a measurable PD-L1 expression result.

- Biomarker subjects: All treated subjects with available biomarker data.
- Outcomes Research Subjects: all treated subjects who have an assessment at baseline (Visit 1 assessment prior to administration of drug) and at least 1 subsequent assessment (for EORTC QLQ-C30 and EQ-5D separately).
- All Re-initiation Treated Subjects: All subjects who received at least one dose of study medication following re-initiation of treatment.

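### By-visit quality-of-life summaries describe whoever is still assessed, so the trend can look favourable even when no subject changes; change from baseline and completion counts should be added

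*Combined protocol and SAP*

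**What the plan says.** Section 1.3.3 lists as an exploratory objective "To evaluate health-related quality of life using a validated instrument", the QLQ-C30, and a second objective for general health status by EQ-5D.

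Section 8.4.6 gives the analysis:
- **QLQ-C30.** Scores are transformed to 0-100. The global health composite and the "remaining EORTC QLQ C-30 scale data will be summarized by time point using descriptive statistics for each cohort assessed". The set is treated subjects "who have an assessment at baseline and at least one follow-up assessment".
- **EQ-VAS.** The overall health state ("EQ-VAS) at each assessment time point will be summarized using descriptive statistics").
- **EQ-5D dimensions.** The proportion with problems at each time point; "Percentages will be based on number subjects assessed at assessment time point". A by-subject EQ-5D listing is also planned.

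Section 8.2 defines the outcomes research population as "all treated subjects who have an assessment at baseline (Visit 1 assessment prior to administration of drug) and at least 1 subsequent assessment".

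On collection, Tables 5.1-2 and 5.1-3 schedule both questionnaires before first dose and then "every 6 weeks when coinciding with clinic visits. Assessed at follow-up visit 1 & 2". Table 5.1-7 adds that "Only EQ-5D Questionnaire is required at Survival Follow-Up Visits".

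Section 8.4.6 states no change from baseline, completion rate, or rule for missing forms or deaths. Sections 8.4.5 and 8.4.7.2 send the reader to the SAP for detail; Section 8.4.6 does not.

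**The concern.** A by-visit mean answers how the subjects assessed at that visit score. The objective asks what happens to quality of life in a treated cohort. The two agree only if the same subjects are assessed throughout, or if those who leave score like those who stay.

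Neither can be assumed here. Under Sections 3.1.4.1 and 3.1.4.7, treatment, and with it the week-numbered visits, ends at progression, toxicity or withdrawal, apart from permitted treatment beyond progression. These events plausibly go with worse scores. Requiring baseline plus one later form does not fix the set across visits: a subject with forms at baseline and Week 6 counts at those two points and is absent at Week 24.

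Setting the Week 24 mean beside the baseline mean therefore mixes change within subjects with change in who is counted, and no planned summary separates them. The treatment cohorts have no untreated comparator that would show the same attrition. Section 5.7 also says that EQ-5D data will feed health economic models, so a selected mean could be carried further than a descriptive table.

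**Working it through.** The documents state no SD, expected change, retention or correlation for either instrument, so there is no figure of the plan's to reproduce. Only the mechanism and a plausible range can be checked.

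**1. Mechanism.** Let every subject's score be constant. Among subjects with baseline and at least one later form, a share d is lost by a later visit. Stayers score S and leavers score S - g.

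- Baseline mean = (1 - d)S + d(S - g) = S - dg
- Later mean = S
- Apparent rise = dg; within-subject change among those assessed = 0

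With S = 75, d = 20% and g = 10, the mean moves from 73 to 75 (+2). With d = 40% and g = 20, it moves from 67 to 75 (+8). With g = 0 it does not move. For an EQ-5D dimension with problems in 30% of stayers and 60% of leavers, and 40% lost, the percentage falls from 0.6 × 30 + 0.4 × 60 = 42% to 30%. S, d and g are assumed. A 20-point gap is 0.8 to 1 SD when the SD is 20-25, so these examples show the mechanism and are not the estimate of size.

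**2. Size with a graded link between score and retention.** Let the baseline score be normal, with correlation ρ to a latent retention variable. The mean score of the top fraction p on retention lies ρ·φ(z_p)/p SDs above the overall mean, where z_p is the normal quantile of p and φ the normal density. Subjects with no later form, taken as the lowest fraction e on retention, are already absent from the planned baseline set. Hence

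shift = ρ × SD × [φ(z_p)/p - φ(z_(1-e))/(1 - e)]

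Assumed inputs: ρ = 0.2 to 0.4; SD = 20 to 25; e = 10% or 20%; p = 70% or 52% of treated subjects still assessed.

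Components of φ/p:
- 90%: 0.1755/0.90 = 0.195
- 80%: 0.2800/0.80 = 0.350
- 70%: 0.3477/0.70 = 0.497
- 52%: 0.3984/0.52 = 0.766

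| Retained | No later form | Bracket | ρ 0.2, SD 20 (× 4) | ρ 0.4, SD 25 (× 10) |
|---|---|---|---|---|
| 70% | 10% | 0.302 | 1.2 | 3.0 |
| 70% | 20% | 0.147 | 0.6 | 1.5 |
| 52% | 10% | 0.571 | 2.3 | 5.7 |
| 52% | 20% | 0.416 | 1.7 | 4.2 |

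The ranges are 0.6-3.0 points at 70% retention and 1.7-5.7 at 52%. With ρ = 0 every entry is zero. If subjects with no later form were left in the baseline mean, 52% retention would give 0.766 × 4 = 3.1 to 0.766 × 10 = 7.7. The two-form rule therefore reduces this particular artefact.

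**3. Direction.** Section 8.4.6 scores functioning and global health so that higher is better, and symptoms so that higher is worse. Functioning, global health and EQ-VAS would drift up; symptom scores and problem percentages would drift down.

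**4. Instrument.** Follow-up visit 1 is about 35 days after last dose and visit 2 about 80 days after that (Table 5.1-7), so these forms do not fill the missing on-treatment weeks. QLQ-C30 then stops. EQ-5D continues at survival visits every 3 months outside the non-MSI-H safety cohort, so progressing subjects who survive still contribute. Section 8.4.6 does not say how off-treatment forms map to time points.

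**The case against.** The strongest reply is that this is a descriptive summary of an exploratory endpoint in small single-arm cohorts, with no test and no planned quality-of-life claim. That stands, and it limits the harm to a misleading trend: no error rate is affected.

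A second reply is that descriptive statistics by time point do not exclude change from baseline or counts, and that a SAP may supply them. The text available has no separate quality-of-life section, so this cannot be ruled out. But Section 8.4.6 names its measures and denominators and does not defer.

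A third is that the by-subject EQ-5D listing shows individual shifts. It does, but a listing is not a summary, and none is stated for QLQ-C30.

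A reader might infer a much larger effect by treating response rates as retention: the 52% design alternative, or 12/40 and 6/40 for Cohort C6. The documents do not support this. Subjects with stable disease stay on treatment, treatment beyond progression is allowed (Sections 3.1.6 and 4.3.8), and the C6 counts are rows of a confidence-interval precision table. For the same reason it is not established that C6 is affected most.

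Nor is the drift always favourable. From 24 months, stopping at maximum clinical benefit (Section 3.1.4.1) can remove subjects who are doing well.

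**Conclusion.** The point holds as a modest, inexpensive improvement. As written, Section 8.4.6 has no summary that separates individual change from change in who is assessed. If leavers score worse than stayers, the by-visit figures drift favourably with nobody improving. The ranges worked out above are a few points on a 0-100 scale. They depend wholly on assumed correlation, SD, retention and share with no later form; the 52% in them is an assumed retention level and not the design's response rate.

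The case is clearest for QLQ-C30 at on-treatment visits and weaker for EQ-5D. It would be wrong to conclude that any observed improvement must be artefact, or that progressing subjects are lost to EQ-5D altogether; the documents support neither.

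**What to change.** In Section 8.4.6 (and the SAP, if it has a matching section), add at each visit:
- within-subject change from baseline for the subjects assessed at that visit, for the QLQ-C30 scales and EQ-VAS;
- the baseline mean of those same subjects;
- the number completing the form, over all treated and over those alive and on treatment.

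For the EQ-5D dimensions, tabulate shifts from baseline level in the same subjects. Keep the planned absolute tables, labelled 'subjects still assessed', and state how follow-up and survival-visit forms are assigned to time points.

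In the constant-score examples above, within-subject change is exactly zero. A mixed model is optional as a supportive analysis; it gains no outcome data from subjects with no post-baseline form.

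The cost is wording and a few more tables from data already collected. One limit remains: change from baseline is still biased if subjects worsen just before they are lost, which is why the completion counts belong beside it.

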8.4.7 Other Analyses

8.4.7.1 Immunogenicity Analyses

Immunogenicity may be reported for ADA positive status (such as persistent positive, transient positive, only last sample positive, baseline positive) and ADA negative status, relative to baseline. In addition, presence of neutralizing antibody may be reported, if applicable. Effect of immunogenicity on safety/efficacy and biomarkers and PK may be explored.

8.4.7.2 Analyses of Re-initiation Treated Subjects

The same methodologies as used for the primary, secondary and exploratory efficacy endpoints will be used to analyze the specific endpoints defined to evaluate the clinical activity of nivolumab monotherapy or combination treatment after re-initiation.

Selected safety analyses will be repeated using the new re-initiation start date or new baseline evaluations as reference, to evaluate the safety of nivolumab monotherapy or combination treatment re-initiation.

All these analyses will be using the population of All Re-initiation Treated Subjects and will be presented by cohort.

In addition, time from initial discontinuation to re-initiation will be described. The detailed of these analyses will be provided in the SAP.

8.5 Interim Analyses

For each treatment arm in the MSI-H cohort (mStage 1 monotherapy and combination therapy, if applicable), one interim analysis of investigator-assessed ORR will be performed on the first 19 treated subjects with confirmed MSI-H CRC. If there are 6 or fewer responses in these first 19 treated subjects, accrual to the corresponding treatment arm will be stopped. Otherwise, approximately 29 additional confirmed MSI-H subjects will be accrued into the corresponding treatment arm to target a total of 48 treated subjects in that arm.

Subjects in mStage 1 or cStage 1 who remain on treatment should complete a 24-week follow up for an assessment of ORR. The final analyses of these initial MSI-H cohort will take place after sufficient follow-up has been achieved for most or all of the subjects (eg, 6 months of treatment for the monotherapy cohort and 9 months of treatment for the combination therapy cohort).

Anticipating a different enrollment rate in cohorts C3-C6, these cohorts will be analyzed independently. Interim analyses will be conducted approximately 6 months after the last subject treated in the corresponding cohort.

In addition, other interim analyses may be conducted to seek initial efficacy signal or for external data disclosure for these cohorts.

9 STUDY MANAGEMENT

9.1 Compliance

9.1.1 Compliance with the Protocol and Protocol Revisions

The study shall be conducted as described in this approved protocol. All revisions to the protocol must be discussed with, and be prepared by, BMS. The investigator should not implement any deviation or change to the protocol without prior review and documented approval/favorable opinion from the IRB/IEC of an amendment, except where necessary to eliminate an immediate hazard(s) to study subjects.

If a deviation or change to a protocol is implemented to eliminate an immediate hazard(s) prior to obtaining IRB/IEC approval/favorable opinion, as soon as possible the deviation or change will be submitted to:

- IRB/IEC for review and approval/favorable opinion
- BMS
- Regulatory Authority(ies), if required by local regulations

Documentation of approval signed by the chairperson or designee of the IRB(s)/IEC(s) must be sent to BMS.

If an amendment substantially alters the study design or increases the potential risk to the subject: (1) the consent form must be revised and submitted to the IRB(s)/IEC(s) for review and approval/favorable opinion; (2) the revised form must be used to obtain consent from subjects currently enrolled in the study if they are affected by the amendment; and (3) the new form must be used to obtain consent from new subjects prior to enrollment.

If the revision is done via an administrative letter, investigators must inform their IRB(s)/IEC(s).

9.1.2 Monitoring

Monitoring details describing strategy, including definition of study critical data items and processes (eg, risk-based initiatives in operations and quality such as risk management and mitigation strategies and analytical risk-based monitoring), methods, responsibilities, and requirements, including handling of noncompliance issues and monitoring techniques (central, remote, or on-site monitoring) are provided in the monitoring plan.

Representatives of BMS must be allowed to visit all study site locations periodically to assess the data quality and study integrity. On site they will review study records and directly compare them with source documents, discuss the conduct of the study with the investigator, and verify that the facilities remain acceptable.

In addition, the study may be evaluated by BMS internal auditors and government inspectors who must be allowed access to CRFs, source documents, other study files, and study facilities. BMS audit reports will be kept confidential.

The investigator must notify BMS promptly of any inspections scheduled by regulatory authorities, and promptly forward copies of inspection reports to BMS.

9.1.3 Investigational Site Training

Bristol-Myers Squibb will provide quality investigational staff training prior to study initiation and prior to implementation of any significant protocol revision. Training topics will include but are not limited to: GCP, AE reporting, study details and procedure, electronic CRFs, study documentation, informed consent, and enrollment of WOCBP.

9.2 Records

9.2.1 Records Retention

The investigator must retain all study records and source documents for the maximum period required by applicable regulations and guidelines, or institution procedures, or for the period specified by BMS, whichever is longer. The investigator must contact BMS prior to destroying any records associated with the study.

BMS will notify the investigator when the study records are no longer needed.

If the investigator withdraws from the study (eg, relocation, retirement), the records shall be transferred to a mutually agreed upon designee (eg, another investigator, IRB). Notice of such transfer will be given in writing to BMS.

